**Skin Prick Test (SPT): 20 Patients**

ABBREVIATIONS

AE	-	Adverse Event
CFR	-	Code of Federal Regulations
CRF	-	Case Report Form
GCP	-	Good Clinical Practice
ESS	-	Erythema Scoring Scale
HIPAA	-	Health Insurance Portability and Accountability Act
ICF	-	Informed Consent Form
IRB	-	Institutional Review Board
PI	-	Principal Investigator or designee
RIPT	-	Repeated Insult Patch Test
SAE	-	Serious Adverse Event
SOP	-	Standard Operating Procedure
SPT	-	Skin Prick Test

DEFINITIONS

**Adverse Event (AE):** Any negative experience that a volunteer has during the course of a clinical trial, including new or worsening symptoms or laboratory abnormalities.

**Belmont Report:** A document entitled "Ethical Principles and Guidelines for the Protection of Human Subjects of Research" that was produced by the National Commission for the Protection of Human Subjects of Biomedical and Behavior Research in 1978. The Belmont Report identifies three fundamental ethical principles for all human subject research: respect for persons, beneficence, and justice.

**Blinding:** When research subjects are unaware of the assigned "treatment." In a single-blinded trial, the subjects do not know what treatment they are receiving. In a double-blinded trial, the subjects and the investigators are unaware of the treatment assigned, as are the monitors and statisticians in some cases.

**Case Report Form (CRF):** A record of information collected on each subject during the clinical trial.

**Clinical Investigation:** A systematic trial designed to evaluate a test material in humans.

**Clinical Research:** A trial in human subjects.

**Clinical Trial:** Any investigation in humans meant to determine properties of a test material.

**Ethics Committee:** An independent group of medical and nonmedical people who verify the integrity of a trial and ensure the safety, integrity, and human rights of the subjects.

**Exclusion Criteria:** Characteristic that would prevent a subject from being eligible to participate in a research trial, as specified in the protocol.

**Good Clinical Practices (GCP):** International ethical and scientific quality standards for the design, conduct, monitoring, recording, auditing, analysis, and reporting of trials.

**Health Insurance Portability and Accountability Act (HIPAA):** Legislation passed in 1996 that includes a privacy rule creating national standards to protect personal health information.

**Inclusion Criteria:** A list of requirements that a subject must meet to be eligible to participate in a research trial, as specified in the protocol.

## 1 PROTOCOL SUMMARY

Title: Skin prick testing of healthy adult volunteers to investigate the potential of allergy to NeoMatriX™ Wound Matrix

Design: Unblinded

Test Articles: 1. NeoMatriX™ Wound Matrix, an investigational device

Duration: 2-3 days

Subjects: Sufficient healthy volunteer subjects so that 20 will complete the study

Observations: Scoring of any skin reactions at 15 minutes, 6 hours and 1-2 days after prick test

Location: Clinical Research Center, UB Clinical and Translational Research Center  
[name]

### 3 **STUDY VISIT CHART**

Day	01	02-03
Prick Test Performed	✓	
Clinically Evaluate Prick Site	15 mins      6 hours	
	✓                      ✓	✓

### 4 **INTRODUCTION, BACKGROUND AND OBJECTIVE**

Skin prick tests for immediate hypersensitivity have been the gold standard as assays for allergies since the 1860s and are currently used by allergists identify allergic reactions to specific allergens. These tests are minimally invasive and are used on patients of all ages from infants to seniors. They have the advantage of being highly sensitive and specific and produce rapid results.

Therapies for facilitating wound healing currently are limited especially with regard to chronic wounds and remain a significant unmet need. Chronic wounds including non-healing skin ulcers such as pressure ulcers, diabetic neuropathic ulcers and vascular insufficiency ulcers, are a source of substantial morbidity and mortality for hospitalized patients and residents of nursing homes. Non-healing and chronic wounds increase the risk of infection and can result in limb amputation and death.

Numerous topical treatments for non-healing wounds have produced mixed results and an ideal treatment remains to be achieved. The test product of this proposal, NeoMatriX™ Wound Matrix, is a wound dressing for the management of wounds, acute and chronic. NeoMatriX™ Wound Matrix has the features of a biocompatible biomaterial. Despite its stringent preparation protocols and having completed a range of biocompatibility testing, prior to utilization in human clinical trials, it remains to be tested in a small pilot study to determine if it can elicit any allergic responses. While it is highly unlikely that any study subject will have de novo, immediate allergic reactions to NeoMatriX™ Wound Matrix, the current protocol is designed to document this and determine whether study subjects may show any delayed allergic reactions.

The objective of this study is to investigate the potential of NeoMatriX™ Wound Matrix to cause an allergic response in healthy volunteers. The biomaterial is applied to the forearm of study subjects, a drop of saline solution is placed on the membrane and using a standard skin prick test device the underlying epidermis is superficially pricked through the overlying membrane. After the test, the area of the skin is observed after 15 minutes and 6 hours to see if a reaction develops. The test site will again be evaluated at 1-2 days after the initial prick test. The skin will be examined for a "wheal"—a raised, itchy bump and surrounding erythematous "flare".

[REDACTED] and flare whose diameter can be measured and exceed a wheal at the negative control by 4 mm. Pricking through a drop of saline serves as a negative control that is not expected to produce a significant wheal and flare. [REDACTED]

[REDACTED], to reiterate, this is completely unanticipated but remains to be proven.

## **5 STUDY DESIGN**

The prick test is not blinded.

## **6 SELECTION OF SUBJECTS**

### **6.1 Screenings**

A sufficient number of subjects will be recruited to ensure a minimum of 20 subjects complete the study. Subjects must satisfy the inclusion and exclusion criteria, must be prepared to accept the prohibitions and restrictions and must give written informed consent.

The suitability of each potential subject will be confirmed before their acceptance by review of a study specific pre-treatment questionnaire.

### **6.2 Inclusion criteria**

- 6.2.1 Healthy volunteers, of either sex, aged at least 18 years.
- 6.2.2 Completed written informed consent and receive a copy of their executed ICF.
- 6.2.3 Volunteers must be capable of understanding and following directions in English.

### **6.3 Exclusion criteria**

- 6.3.1 Pregnancy or lactation.
- 6.3.2 Inadequate or non-existent contraception (women of child bearing potential only).
- 6.3.3 A current skin disease of any type apart from mild facial acne (e.g. eczema, psoriasis).
- 6.3.4 Heavy alcohol consumption.
- 6.3.5 Current use or history of repeated use of recreational drugs.
- 6.3.6 A febrile illness lasting more than 24 hours in the six days prior to test.
- 6.3.7 Significant past medical history of hepatic, renal, cardiac, pulmonary, digestive, hematological, neurological, locomotor or psychiatric disease.
- 6.3.8 [REDACTED]

6.3.10 [REDACTED]

[REDACTED] erials.

6.3.12 Current treatment by a physician for allergy unless physician consulted by Investigator and participation approved.

6.3.13 Participation in a repeat insult patch test (RIPT), skin prick test (SPT) or follow-up work within the last month.

6.3.14 Sensitization or questionable sensitization in a RIPT or SPT.

6.3.15 Recent immunization (less than 10 days prior to prick test).

6.3.16 A medical history indicating atopy or severe dermatographism.

#### **6.4 Prohibitions and restrictions for the duration of the study**

6.4.1 No use of aspirin or non-steroidal anti-inflammatory or corticosteroid drugs for the duration of the study.

6.4.2 [REDACTED]

6.4.3 [REDACTED]

### **METHOD**

**7.1 Test Articles – NeoMatriX™, extracellular matrix xenograft, 8mm disc**

**7.2 Negative Skin Test Control– sterile normal saline**

**7.3 Positive Skin Test Control – Sterile histamine** [REDACTED]

#### **7.4 Materials**

- Test article NEOMATRIX™ 8mm disc
- Positive control solution
- Negative control solution
- [REDACTED]
- Sharps container for disposal of picks
- Marker pen for the skin
- Ruler for measuring reactions
- Sterile cotton balls for wiping skin
- Gloves (latex-free)
- Recording sheets, Case Report Forms
- Syringes and needles
- Cetirizine 10 mg tablets
- Hydrocortisone cream 1%

### 7.5 Devices used for skin prick testing

- [REDACTED]

### 7.6 Procedure

The subject needs is placed in a comfortable position with volar surface of the forearm

[REDACTED] The room should be private and at a comfortable temperature. It is advisable to provide the patient with a magazine or something to occupy themselves for the 15-20 minutes that is required for the test (and to distract them from any discomfort).

The test area should be clean, free from moisturizers and area for skin pricks should be more than 5 cm from the wrist and 3 cm from the antecubital fossa and marked by numbers on the skin to identify the test article, negative control and positive control. Pricks should be made immediately adjacent to the numbers to avoid confusion between allergens. Prick tests should be at least 2 cm apart to avoid overlapping reactions and false-positive results.

[REDACTED]

Positive and negative controls will be applied directly with the Picks.

A separate Pick is used to prick each site. For example, there should be 3 Picks used per subject, one for each test site. Prick each site separately.

### 7.7 Grading of Test Sites - Reading Results

- Initial reading after 15 minutes looking for the presence or absence of a wheal and flare at all three sites and measuring the diameter of both the wheal and flare if present. The wheal at the positive control must exceed a wheal at the negative control by 4 mm.
- A second reading is conducted about 6 hours after the SPT administration and similar measurements are taken.
- The subjects return to the office 1-2 days after the initial administration for a third test reading and measurements.
- A positive reaction is present when there is a measurable wheal of >3 mm . Small wheals are confirmed by palpation. A flare alone is measured but is not of any clinical significance.

### 7.8 Characteristics of Wheal and Flare

Wheals are determined by palpation or oblique lighting and the diameter is measured in mm. If the wheal is not asymmetrical two diameters are measured (smallest and largest) and an average value is calculated. Flares, areas of erythema, are similarly measured but are not considered clinically significant.

## 8 SAFETY - ADVERSE EVENTS

### 8.1 Relationship to Test Material

The relationship or association of the AE to the test material will be characterized as unlikely, possible or probably. Assessments shall be recorded on the CRF.

Causality Term	Assessment Criteria
Probable	Event or laboratory test abnormality, with plausible time relationship to test material exposure
	Unlikely to be attributed to condition (or disease) or other products in use by subject
	Response to withdrawal clinically reasonable
	Rechallenge satisfactory or not required
Possible	Event or laboratory test abnormality, with reasonable time relationship to test material intake
	Could also be explained by condition (or disease) or other products in use by subject
Unlikely	Event or laboratory test abnormality, with a time to test material intake that makes a relationship improbable (but not impossible)
	Condition (or disease) or other products provide plausible explanations

For safety analyses, AEs that are classified as a possible or probable association to a test material shall be considered test material-related AEs.

Follow-up of the AE, after the date of discontinuation of exposure to test material is required if the AE or its sequelae persist. Follow-up is required until the event or its sequelae resolve or stabilize at a level acceptable to the PI and to the Medical Monitor.

### 8.2 Severity of Adverse Events

The severity of each AE will be graded using the following criteria:

Grade	Description
1	Mild – Minor AEs requiring no specific medical intervention including asymptomatic laboratory findings only, or finding of marginal clinical relevance
2	Moderate – AEs including urticaria requiring minimal, local, and/or noninvasive intervention
3	Severe – Severe and undesirable AEs involving significant symptoms requiring hospitalization or invasive intervention; transfusion; elective interventional radiological procedure; or therapeutic endoscopy or operation

4	Life-threatening or debilitating – AEs complicated by acute, life-threatening metabolic or cardiovascular complications such as circulatory failure, hemorrhage, or sepsis. Also, life-threatening physiologic consequences; need for intensive care or emergent invasive procedure; emergent interventional radiological procedure, therapeutic endoscopy or operation.
5	Death

If the Grade changes within a day, the maximum Grade shall be recorded.

If the Grade changes over a longer period of time, the changes shall be recorded as separate events (having separate onset and stop dates for each grade).

### 8.3 Serious Adverse Events

An SAE is defined as any AE that suggests a significant clinical hazard, contraindication, side effect, or precaution. This includes any event which:

- Results in death
- Is life-threatening
- Results in persistent or significant disability/incapacity
- Results in or prolongs an existing inpatient hospitalization
- Results in a congenital anomaly/birth defect
- Is an important medical event based on medical judgment, which jeopardizes the subject and requires medical or surgical intervention to prevent one of the outcomes listed above.

The PI will evaluate all serious AEs as to their intensity, relation to test material, outcome, and action taken.

#### Management of Adverse Events

No adverse reaction is anticipated. The patient will be evaluated at 15 minutes after SPT and then again at 6 hours after SPT. Minor adverse events (e.g. itching at the skin test site) will be examined by the nursing staff of the CRC; the PI will be contacted as needed.

- Over-the-counter (OTC) antihistamines will be given, which relieve minor symptoms. Antihistamines prevent symptoms such as hives by blocking histamine receptors.
- Persistent itching, swelling or redness, will be reduced with ice and at the test site we shall apply 1% hydrocortisone cream one time.
- Should the subject develop urticaria they will be provided with a 5 day course of antihistamine (10 mg cetirizine orally once daily)

While serious adverse events are not anticipated the most likely serious event would be a systemic allergic reaction or anaphylaxis which would most likely occur within 20 minutes while the subject is under close evaluation at the CRC.

- The subject will be assisted to lie on their back with feet raised about 12 inches, clothing loosened to ease breathing, covered with a blanket and coached to stay calm. They will be turned on their side if vomiting or bleeding.
- Epinephrine (adrenaline) may be used, depending on the severity.

- Should anaphylaxis occur Epinephrine 1:1000 will be administered immediately by intramuscular injection and repeated every 10 min. as needed. The PI will be summoned stat and the subject will be transported to the Emergency Department of the Buffalo General Medical Center located on the ground floor of the same building housing the Clinical Research Center.

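### Antihistamine is provided for minor events such as test-site itch, but the visible text does not say how to handle a negative 6-hour or 1-2-day reading taken after treatment

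*Protocol*

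**What the plan says.** **Treatment.** Protocol section 8, Management of Adverse Events, opens with the 15-minute and 6-hour evaluations and then says: "Minor adverse events (e.g. itching at the skin test site) will be examined by the nursing staff of the CRC". The first bullet is "Over-the-counter (OTC) antihistamines will be given, which relieve minor symptoms", and it adds: "Antihistamines prevent symptoms such as hives by blocking histamine receptors". The second covers lasting local signs: "Persistent itching, swelling or redness, will be reduced with ice and at the test site we shall apply 1% hydrocortisone cream one time". A 5-day course of cetirizine 10 mg once daily is reserved for urticaria. Section 7.4 lists "Cetirizine 10 mg tablets", the only oral antihistamine visible among the materials.

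**Sites.** Under section 7.6 each subject is pricked at three sites. One is the control in section 7.3, "Positive Skin Test Control – Sterile histamine". Section 7.7 requires a response there: "The wheal at the positive control must exceed a wheal at the negative control by 4 mm". Section 4 describes a wheal as raised and itchy.

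**Readings.** Section 7.7 sets readings at 15 minutes, about 6 hours and 1-2 days. One positivity rule serves all three: "A positive reaction is present when there is a measurable wheal of >3 mm". A flare alone has no clinical significance. Section 4 makes delayed reactions part of the study's purpose, and section 9.1 says that wheal/flare is the only physiological measure.

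**The concern.** The drug offered for a minor symptom acts, on the protocol's own account, against the sign that is the endpoint. The histamine control is meant to raise a wheal, so it can produce the symptom that prompts treatment in a subject whose test-article site shows nothing. An oral drug given for that itch also reaches the test-article site.

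Only the 6-hour and 1-2-day readings can show a delayed reaction, and these are the readings that follow such treatment. If a treated negative is tallied with the untreated ones, any error favours the result the sponsor expects. A report of 0 of 20 would not show how many of the 20 were read under treatment.

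**Working it through.** The plan gives no figure on this point. The sample-size statement in section 9.1 contains no reaction rate or treated share and does not enter the check. The main check sets the sections side by side.

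1. **Trigger.** Management of Adverse Events gives test-site itch as its example of a minor event. It neither limits this to the test-article site nor exempts the histamine site.
2. **Source of itch.** Sections 7.3, 7.6 and 7.7 give every subject a histamine prick, with a wheal required there. Section 4 calls wheals itchy. Itch without any test-article reaction is therefore foreseeable.
3. **Action on the endpoint.** Management of Adverse Events attributes the effect of antihistamines to histamine-receptor blockade and says they prevent hives. The endpoint is a wheal.
4. **Timing.** A drug given just after the 15-minute reading precedes the 6-hour reading. Reading first therefore protects the reading in hand but not the later ones. Cetirizine dosed once daily is consistent with an effect at 6 hours. However, the protocol states no duration of effect and does not say that cetirizine is the drug used for minor events.
5. **Classification.** Section 7.7 has no flag or separate category for a reading after treatment. The positive-control criterion is stated with the 15-minute reading, and none is stated for later readings that might reveal suppression.

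Who can be affected:

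| Situation | Delayed test-article result |
|---|---|
| Test-article wheal >3 mm read before treatment | Stays positive |
| Ice or steroid on a control site only | Not affected |
| Oral antihistamine, no positive test-article reading before it | A later wheal could be suppressed |
| Ice or steroid on the test-article site, no positive reading before it | A later wheal could be suppressed |

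**Illustration of size.** With 0 positives in m informative readings, the exact one-sided 95% upper confidence limit p solves (1 − p)^m = 0.05, so p = 1 − 0.05^(1/m).

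- m = 20 (the planned number of completers, all untreated): 1 − 0.05^(1/20) = 1 − 0.8609 = 13.9%.
- m = 15 (assumed: 5 of 20 treated, their negatives taken to carry no information): 1 − 0.05^(1/15) = 1 − 0.8190 = 18.1%.

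The difference is 18.1 − 13.9 = 4.2 percentage points. The 15 is an assumption, since the protocol gives no treated share, and treating those negatives as wholly uninformative is the worst case for that count.

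**The case against.** The other side has real force on four points.

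- **Treatment is not certain.** Section 8.2 defines Grade 1 events as minor and needing no specific medical intervention. Management of Adverse Events has nurses examine minor events and call the investigator as needed. It also anticipates no adverse reaction, which sits oddly with treating an expected control wheal as one. A reader might infer that every subject with control-site itch must be medicated. The documents do not support that; they leave it possible. This part of the objection stands.
- **Suppression is not shown.** The antihistamine for minor symptoms is unnamed, no duration is given, and nothing establishes that one dose would affect the 1-2-day reading. This stands too, and limits the claim mainly to 6 hours.
- **Redaction.** Restrictions 6.4.2 and 6.4.3, part of the procedure in section 7.6 and interpretive text in section 4 are blacked out. A read-first step or a drug restriction could sit there, so its absence cannot be asserted. However, the grading rules in section 7.7 show no redaction, and they make no provision for treated readings.
- **Leave it to the analysis plan or CRF.** This is weaker. When sites are read relative to treatment is a matter of conduct, and section 9.1 says that no statistical analysis will be performed.

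**Conclusion.** The point holds in a limited form. On the visible text, a subject without a positive test-article reading may be given an antihistamine for minor itch, including itch from the histamine control, and then be read as having no delayed reaction because a wheal was suppressed. The risk is most plausible at 6 hours and less certain at 1-2 days. It can only push the delayed result toward none. Frequency and size are unknown.

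A reader might infer from the illustration that the true delayed-reaction rate lies between 13.9% and 18.1%. It does not say that: both are upper confidence limits under 0 positives, and the second rests on an assumed count. Nor do the documents support concluding that the delayed readings as a whole are invalid, because positives survive and untreated readings are unaffected.

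Severity is minor to moderate: a one-directional bias on a stated aim in a 20-subject study, conditional on treatment being given.

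**What to change.** **Section 7.7 and Management of Adverse Events.** Add: *Where care allows, all three sites are measured before any antihistamine, ice or topical steroid is given. The drug, time and site treated are recorded on the CRF.* If redacted text already requires this reading, a cross-reference from Management of Adverse Events is enough for that part.

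**Sections 7.7 and 9.1.** Add: *Every positive reading is kept. A negative test-article reading taken after an oral antihistamine, or after ice or topical steroid at the test-article site, is reported separately from untreated negatives. Local treatment of a control site alone does not change the status of the test-article reading. The number of untreated test-article readings at T2 and T3 is stated. Treated subjects still count as completers.*

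The cost is protocol wording and three CRF fields (drug, time, site treated). Needed care is neither withheld nor delayed, and recruitment does not change because treated subjects remain among the 20. The downside is fewer clean delayed readings behind the headline result.
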